Objectives	
Primary Objectives
 
1. To estimate the mean difference between Sites treated with laser-assisted 5-FU delivery versus laser-assisted TAC in the changes from the first POSAS score (before initiating treatment series) to the final POSAS score.2. To estimate the mean difference between Sites treated with laser-assisted 5-FU delivery versus laser-assisted TAC in the modified Hamilton score at the final visit 
Secondary Objectives
 
The secondary objective is to assess the differences between Sites treated with laser-assisted 5-FU delivery versus laser-assisted TAC in the changes in size of keloids post treatment
 
Exploratory objective
 
The exploratory objective is to assess the differences between Sites treated with laser-assisted 5-FU delivery versus laser-assisted TAC in the patients subjective experiences, such as pain related to treatment, healing time.

Methodology	Triple-blinded prospective study

CONFIDENTIAL

This material is the property of the NYU School of Medicine and Langone Medical Center. Do not disclose or use except as authorized in writing by the study sponsor

Interventional Template Version: 11 JAN 2019

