3.2 Secondary Objective

The secondary objective is to assess the differences between both Sites in change in size of keloids post treatment.

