4.2.2 Secondary Study Endpoint

The secondary endpoint is measurements of the scar in both Sites of the keloid. The measurements will be calculated as the total volume (length x width x height) in cm³ of the scar, or length x width in cm² if the scars are flush with the surrounding skin scar surface in the two Sites of the keloid.

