5.1 Inclusion Criteria

In order to be eligible to participate in this study, an individual must meet all of the following criteria:

1. Age 18-89
2. Has one large keloid scar or at least two similar but separate keloid scars
3. Keloid present for at least 1 year

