7.2.1 Treatment Visits

Visits 1 - 4

- Urine pregnancy test if female of child-bearing age. (visits 2-4)
- Physical examination of lesion of interest.
- Photography of lesion (keloid) of interest, taken before any treatment is performed
- Measurement (height, length, width) of lesion (keloid) of interest performed at the start of the visit, before treatment
- Completion of POSAS (including monitoring of adverse events) by patient and providers at the start of the visit
- Administer the study treatment (to be performed by PI): laser assisted drug-delivery treatment of both 5-FU and TAC.
- Monitoring of adverse events
- Patients will be asked about side effects (non-serious adverse events) from laser treatment on visits 2-4
- Patients will be asked to grade their post-procedure pain on a scale of 1 to 10 on visits 2-4
- Patients will be asked which side healed faster after the laser treatment on visits 2-4
- Post-treatment instructions will be provided to patients on an after-treatment instruction sheet: gentle cleansing of area with soap and water twice a day, apply petrolatum jelly and keep area covered for 1 week, avoid sun exposure to treated area(s) for study duration.
- Visits will take place every 4 weeks ± 1 week.

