10.2.4 Secondary Analysis

The measurements of the scar will be defined as the total volume (length x width x height) in cm^3 of the scar, or length x width in cm^2 if the scars are flush with the surrounding skin scar surface.

Measurements of the scar will be summarized by visit and compared between the two Sites of the keloid.

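### The secondary objective is change in keloid size, but the endpoint and analysis compare size itself by visit, with no use of the Visit 1 measurement and no named visit or test

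*Combined protocol and SAP*

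**What the plan says.** Section 3.2 sets the aim: to "assess the differences between both Sites in change in size of keloids post treatment". The Protocol Summary frames the same aim as laser-assisted 5-FU versus laser-assisted TAC "in the changes in size of keloids post treatment".

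The endpoint in 4.2.2 is different: "The secondary endpoint is measurements of the scar in both Sites of the keloid". Section 10.2.4 defines the variable ("The measurements of the scar will be defined as the total volume (length x width x height", in cm³, or length by width in cm² for a flush scar) and then gives the whole analysis in one sentence: "Measurements of the scar will be summarized by visit and compared between the two Sites of the keloid". The Protocol Summary repeats it.

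For size, no section gives a change score, a baseline covariate, a comparison visit or a test. Section 10.2.3, immediately before, gives all of these except the covariate for POSAS: change from first to final score, by a two-sided paired Wilcoxon signed-rank test.

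The eligible lesions (5.1) are described thus: "Has one large keloid scar or at least two similar but separate keloid scars". Section 4.1 prefers two separate scars, and no size tolerance is stated. The pre-treatment size is collected. Section 7.2.1, covering Visits 1 to 4, lists "Measurement (height, length, width) of lesion (keloid) of interest performed at the start of the visit, before treatment", and 7.2.2 repeats the measurement at Visit 5.

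**The concern.** A difference between Sites in Visit 5 volume mixes two things: how each keloid responded and how large each was at the start. Only the first is the objective. In a given participant, the Site that began larger can still be larger at Visit 5 after the better response. Across 20 participants these starting differences inflate the variance of the paired comparison. A by-visit comparison also includes Visit 1, which is before treatment and holds no drug effect.

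With no visit, scale or test fixed, the choice among them would be made after the data are seen. Size is the trial's only secondary outcome, and section 2.1 names the caliper measurements as its measure of effectiveness.

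**Working it through.** **1. The plan's own power figure.** None exists for size. The only one is the POSAS table in 10.1 (20 pairs, two-sided 0.05, 80% power). There SD = 2 × 27 × (1 − ρ), giving 48.6, 40.5, 27.0, 13.5 and 5.4. A paired t calculation with the Wilcoxon efficiency factor 3/π gives a detectable standardised difference of 0.6777. Multiplied by those SDs, it gives 32.94, 27.45, 18.30, 9.15 and 3.66, against the stated 33.0, 27.5, 18.4, 9.2 and 3.7. The table reproduces, but it says nothing about size.

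**2. When does using Visit 1 help?** Assume equal SD *s* at both visits, first-to-final correlation *r* and between-Site correlation *c*.

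- Variance of the raw final difference: 2s²(1 − c)
- Variance of the difference in change: 4s²(1 − r)(1 − c)
- Ratio of SDs, raw to change: 1/√(2(1 − r))
- SD after baseline adjustment relative to raw: √(1 − r²)

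The documents give no *r* for size, so the range used for POSAS is borrowed as an assumption:

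| r | SD raw / SD change | Power of raw final comparison when change has 80% | SD adjusted / SD raw |
|---|---|---|---|
| 0.1 | 0.75 | 96% | 0.99 |
| 0.25 | 0.82 | 93% | 0.97 |
| 0.5 | 1.00 | 80% | 0.87 |
| 0.75 | 1.41 | 51% | 0.66 |
| 0.9 | 2.24 | 24% | 0.44 |

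A simple change score gains only if r exceeds 0.5. Baseline adjustment has a smaller SD than the raw comparison at every r shown.

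**3. Illustration on volume.** All inputs are assumptions: 20 pairs, log-normal volumes, between-participant log-SD 0.8, response log-SD 0.25 per Site, 30% shrinkage common to both drugs and a further 30% with one drug. Per-Site baseline log-SD is 0.1, 0.2, 0.3, 0.5 or 0.7. The median relative difference within a pair is exp(0.6745 × √2 × SD) − 1, that is 10%, 21%, 33%, 61% or 95%. Simulated power, signed-rank test:

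| Caliper log-SD | Raw Visit 5 volume, baseline log-SD 0.1 / 0.2 / 0.3 | Percent change from Visit 1 |
|---|---|---|
| 0 | 94 / 84 / 69% | about 99% |
| 0.15 | 88 / 77 / 63% | about 88% |
| 0.25 | 73 / 65 / 54% | about 65% |
| 0.35 | 58 / 52 / 44% | about 44% |

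Without caliper error, raw power falls further, to 40% and 25%, at baseline log-SD 0.5 and 0.7. Over the whole grid:

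- raw Visit 5 volume: about 22 to 95%
- percent change: about 44 to 99%
- baseline-adjusted log size: about 51 to 99%, and above raw in every cell

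Part of the last gain comes from the log scale, which stops a few large keloids from dominating.

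**4. Bias check.** With equal drug effects and randomised Sites, the raw comparison rejects in about 4 to 5% of simulated trials.

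**The case against.** Section 10.2.4 never says raw or absolute, and names no test. Read beside 3.2, it could be taken to mean that changes are compared. Section 2.1 speaks of measurements before, during and after treatment, and 10.2.2 summarises baseline scar characteristics, so an imbalance would be visible. This stands in part: the plan is silent on baseline and has not ruled it out. But silence leaves the analysis undefined, and the plain sense of comparing the defined volume by visit is size itself. The same correction is needed either way.

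A reader might infer that the comparison is biased against whichever drug falls on the larger keloid. The documents do not support that: 4.1 and 10.1.1 randomise drug to Site. Section 6.2.1 does give a fixed drug-to-Site assignment, which conflicts with 10.1.1, and the two must be reconciled. If assignment were in fact fixed, any systematic size difference between Sites would be confounded with drug. In a separate illustration (response log-SD 0.15, baseline log-SD 0.25 per Site), with Site A 20% larger and equal drug effects, raw volume gave 40% false positives and the log ratio about 5%.

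A reader might also infer that most of the power is lost and that percent change restores it. Neither holds generally. Raw power below about 50% without caliper error needs pairs that typically differ by 61% or more, whereas eligibility asks for similar keloids. Percent change also carries the error of the Visit 1 measurement. At caliper log-SD 0.35 with closely matched keloids, it has about 44% power against 58% for raw. Absolute change is no safer: its power depends heavily on the common shrinkage (96 to 89% with none, 91 to 18% with 50%, no caliper error, over the same baseline range).

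**Conclusion.** The mismatch is in the text, and no other section resolves it. The objective is change in size; the endpoint and analysis are size, with no baseline, visit or test. That finding needs no assumption about variability.

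The consequence is lost precision and chance imbalance, with type I error intact, provided drug is randomised to Site. How much precision is lost cannot be stated from the documents. The 22 to 95% and 51 to 99% ranges rest on the assumed effect, response spread, baseline spread and caliper error in step 3. They show that ignoring Visit 1 can be costly and that baseline adjustment on the log scale is the more dependable choice across those inputs. This is a secondary outcome with no power claim, and the necessary data are already collected, so the point should be corrected but does not threaten the primary analysis.

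**What to change.** In 4.2.2, 10.2.4 and the Protocol Summary:

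- Define the secondary outcome as size at Visit 5 relative to Visit 1 for each Site, in one unit at both visits. Settle the cm³/cm² switch first, because change cannot be computed across units if a scar becomes flush.
- Name Visit 5 as the single comparison time, and compare by drug rather than by Site letter.
- As the main analysis, regress the within-participant difference in log Visit 5 size (5-FU minus TAC) on the difference in log Visit 1 size. The intercept is the drug difference at equal starting size. Report its estimate, confidence interval and test.
- Make a signed-rank test on the log ratio or percent change a sensitivity analysis.
- Keep by-visit raw sizes as description.
- Reconcile 6.2.1 with 4.1 and 10.1.1 on allocation.

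The cost is wording and slightly more analysis work; no new measurement is needed. The regression adds a model assumption with only 20 pairs, and scars of zero or near-zero size need a stated handling on the log scale.

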10.2.5 Exploratory Analysis

Patient's subjective experiences will be summarized and compared between both Sites of the keloid as follows:

CONFIDENTIAL

This material is the property of the NYU School of Medicine and Langone Medical Center. Do not disclose or use except as authorized in writing by the study sponsor
Interventional Template Version: 11 January 2019

1. Patient perceived side effects after each treatment will be summarized by type (dyspigmentation, pain, itch, swelling), visit (1, 2, 3, 4) and treatment Site (A, B).
2. Pain after each laser treatment will be summarized by grade (scale of 1 to 10 (10 being the worst pain)), visit (1, 2, 3, 4) and treatment Site (A, B).
3. Speed of healing after completion of laser treatments at final visit (visit 5) will be compared between both Sites (Site A healed faster than Site B, Site B healed faster than Site A, Same speed of healing in both Sites)

Source data is all information, original records of clinical findings, observations, or other activities in a clinical trial necessary for the reconstruction and evaluation of the trial. Source data are contained in source documents. Examples of these original documents, and data records include: hospital records, clinical and office charts, laboratory notes, memoranda, subjects' diaries or evaluation checklists, pharmacy dispensing records, recorded data from automated instruments, copies or transcriptions certified after verification as being accurate and complete, microfiches, photographic negatives, microfilm or magnetic media, x-rays, subject files, and records kept at the pharmacy, at the laboratories, and at medico-technical departments involved in the clinical trial. It is acceptable to use CRFs as source documents. If this is the case, it should be stated in this section what data will be collected on CRFs and what data will be collected from other sources.

The study case report form (CRF) is the primary data collection instrument for the study. All data requested on the CRF must be recorded. All missing data must be explained. If a space on the CRF is left blank because the procedure was not done or the question was not asked, write "N/D". If the item is not applicable to the individual case, write "N/A". All entries should be printed legibly in black ink. If any entry error has been made, to correct such an error, draw a single straight line through the incorrect entry and enter the correct data above it. All such changes must be initialed and dated. DO NOT ERASE OR WHITE OUT ERRORS. For clarification of illegible or uncertain entries, print the clarification above the item, then initial and date it.

CONFIDENTIAL

This material is the property of the NYU School of Medicine and Langone Medical Center. Do not disclose or use except as authorized in writing by the study sponsor
Interventional Template Version: 11 January 2019

Access to study records will be limited to IRB-approved members of the study team. The investigator will permit study-related monitoring, audits, and inspections by the IRB/EC, government regulatory bodies, and University compliance and quality assurance groups of all study related documents (e.g. source documents, regulatory documents, data collection instruments, study data etc.). The investigator will ensure the capability for inspections of applicable study-related facilities (e.g. pharmacy, diagnostic laboratory, etc.).

Participation as an investigator in this study implies acceptance of potential inspection by government regulatory authorities and applicable University compliance and quality assurance offices.

11 Quality Assurance and Quality Control

QC procedures will be implemented beginning with the data entry system and data QC checks that will be run on the database will be generated. Any missing data or data anomalies will be communicated to the site(s) for clarification/resolution.

12 Ethics/Protection of Human Subjects

12.1 Ethical Standard

The investigator will ensure that this study is conducted in full conformity with Regulations for the Protection of Human Subjects of Research codified in 45 CFR Part 46, 21 CFR Part 50, 21 CFR Part 56, and/or the ICH E6.

12.2 Institutional Review Board

The protocol, informed consent form(s), recruitment materials, and all participant materials will be submitted to the IRB for review and approval. Approval of both the protocol and the consent form must be obtained before any participant is enrolled. Any amendment to the protocol will require review and approval by the IRB before the changes are implemented to the study. All changes to the consent form will be IRB approved; a determination will be made regarding whether previously consented participants need to be re-consented.

12.3 Informed Consent Process

12.3.1 Consent and Other Informational Documents Provided to Participants

Consent forms describing in detail the study agent, study procedures, and risks are given to the participant and written documentation of informed consent is required prior to starting intervention/administering study product. The consent form will be submitted with this protocol.

12.3.2 Consent Procedures and Documentation

Informed consent is a process that is initiated prior to the individual's agreeing to participate in the study and continues throughout the individual's study participation. Extensive discussion of risks and possible benefits of participation will be provided to the participants and their families. Consent forms will be IRB-approved and the participant will be asked to read and review the document in addition to the key information sheet. The investigator (PI and/or co-investigator) will explain the research study to the participant and answer any questions that may arise. Informed consent to review medical records to assess exclusion and inclusion criteria will take place over the phone and subject privacy will be protected. All participants will receive a verbal explanation in terms suited to their comprehension of the purposes, procedures, and potential risks of the study and of their rights as research participants. At the screening visit, participants will have the opportunity to carefully review the written consent form and ask questions prior to signing. The participants should have the opportunity to discuss the study with their surrogates or think about it prior to agreeing to participate. The participant will sign the informed consent document prior to any procedures being done specifically for the study. The participants may withdraw consent at any time throughout the course of the trial. A copy of the signed informed consent document

CONFIDENTIAL

This material is the property of the NYU School of Medicine and Langone Medical Center. Do not disclose or use except as authorized in writing by the study sponsor
Interventional Template Version: 11 January 2019

will be given to the participants for their records. The rights and welfare of the participants will be protected by emphasizing to them that the quality of their medical care will not be adversely affected if they decline to participate in this study.

A copy of the signed informed consent document will be stored in the subject's research record. The consent process, including the name of the individual obtaining consent, will be thoroughly documented in the subject's research record. Any alteration to the standard consent process (e.g. use of a translator, consent document presented orally, etc.) and the justification for such alteration will likewise be documented.

12.4 Participant and Data Confidentiality

Information about study subjects will be kept confidential and managed according to the requirements of the Health Insurance Portability and Accountability Act of 1996 (HIPAA). Those regulations require a signed subject authorization informing the subject of the following:

- What protected health information (PHI) will be collected from subjects in this study
- Who will have access to that information and why
- Who will use or disclose that information
- The rights of a research subject to revoke their authorization for use of their PHI.

In the event that a subject revokes authorization to collect or use PHI, the investigator, by regulation, retains the ability to use all information collected prior to the revocation of subject authorization. For subjects that have revoked authorization to collect or use PHI, attempts should be made to obtain permission to collect at least vital status (i.e. that the subject is alive) at the end of their scheduled study period.

Participant confidentiality is strictly held in trust by the participating investigators and their staff. This confidentiality is extended to cover testing of biological samples and genetic tests in addition to the clinical information relating to participants. Therefore, the study protocol, documentation, data, and all other information generated will be held in strict confidence. No information concerning the study or the data will be released to any unauthorized third party.

The study monitor, representatives of the IRB or pharmaceutical company supplying study product may inspect all documents and records required to be maintained by the investigator, including but not limited to, medical records (office, clinic, or hospital) and pharmacy records for the participants in this study. The clinical study site will permit access to such records.

The study participant's contact information will be securely stored at each clinical site for internal use during the study. At the end of the study, all records will continue to be kept in a secure location for as long a period as dictated by local IRB and Institutional regulations.

Study participant research data, which is for purposes of statistical analysis and scientific reporting, will be transmitted to and stored at NYU Langone Medical Center. This will not include the participant's contact or identifying information. Rather, individual participants and their research data will be identified by a unique study identification number. The study data entry and study management systems used by clinical sites and by NYU Langone Medical Center research staff will be secured and password protected. At the end of the study, all study databases will be de-identified and archived at the NYU Langone Medical Center. Photographs will be non-identifiable in content and labeling. Photographs will be stored on a secured drive on a password protected computer in [name] and only representative non-identifiable photos will be used for publication and/or teaching purposes.

CONFIDENTIAL

This material is the property of the NYU School of Medicine and Langone Medical Center. Do not disclose or use except as authorized in writing by the study sponsor
Interventional Template Version: 11 January 2019

13 Data Handling and Record Keeping

13.2 Study Records Retention

Study documents will be retained for 5 years after final reporting/publication.

13.3 Protocol Deviations

A protocol deviation is any noncompliance with the clinical trial protocol, GCP, or Manual of Procedures (MOP) requirements. The noncompliance may be either on the part of the participant, the investigator, or the study site staff. As a result of deviations, corrective actions are to be developed by the site and implemented promptly.

These practices are consistent with ICH E6:

- 4.5 Compliance with Protocol, sections 4.5.1, 4.5.2, and 4.5.3
- 5.1 Quality Assurance and Quality Control, section 5.1.1
- 5.20 Noncompliance, sections 5.20.1, and 5.20.2

The PI/study will identify and report deviations within 30 working days of identification of the protocol deviation, or within 30 working days of the scheduled protocol-required activity per IRB guidelines.

All protocol deviations will be addressed in study source documents.

